APPENDIX B DETAILED DESCRIPTION OF THE ASSAYS PERFORMED IN THE STUDY

Neutralisation assay

The serum neutralisation assay is a functional assay that measures the ability of serum antibodies to neutralise the cytopathic effects of RSV (for example, strains A and B) on the host cell line, hence RSV replication.

First, virus neutralization is performed by incubating a fixed amount of RSV-A long strain (ATCC No. VR-26) with serial dilutions of the test serum. Then, the serum-virus mixture is transferred onto a monolayer of Vero cells (African Green Monkey, kidney, *Cercopithecus aethiops*, ATCC CCL-81) and incubated for three days to allow infection of Vero cells by non-neutralized viruses and the formation of plaques in the cell monolayer. Following the fixation period, RSV-infected cells are detected using a primary antibody directed against RSV (anti-RSV IgG) and a secondary antibody conjugated with fluorescein isothiocyanate (FITC), allowing the visualization of plaques by immunofluorescence. Viral plaques are counted using an automated microscope coupled to an image analyzer (Scanlab system with Axiovision software). For each serum dilution, a ratio, expressed as a percentage, is calculated between the number of plaques at that dilution and the number of plaques in the virus control wells (no serum added). The serum neutralizing antibody titer is expressed in ED60 (Estimated Dilution 60) and corresponds to the inverse of the interpolated serum dilution that yields a 60% reduction in the number of plaques compared to the virus control wells.

Anti-NEO ELISA

The anti-NEO ELISA assay is based on a direct ELISA format. This ELISA assay allows the quantification of NEO-specific IgG antibodies in human serum samples.

In summary, full-length recombinant human NEO is adsorbed onto a 96-well polystyrene microplate. After washing and blocking steps and dilutions of serum samples, controls and standards are added to the coated microplate. The standard curve is prepared with known concentrations of affinity purified rabbit anti-NEO polyclonal antibodies. After incubation, the microplate is washed to remove unbound primary antibodies. Bound primary antibodies are detected by the addition of a purified monoclonal mouse anti-human IgG antibody, conjugated to horse-radish peroxidase (HRP). This conjugated antibody cross-reacts with rabbit IgG (e.g. anti-NEO antibodies from rabbit used as positive control and standards) and detects human and rabbit IgG with a comparable sensitivity. Unbound HRP is removed by washing. Bound antibodies are quantified by the addition of the HRP substrate, tetramethylbenzidine (TMB), whereby a coloured product develops proportionally to the amount of anti-NEO antibodies present in the serum sample. The optical density (OD) of each sample dilution is then interpolated on a standard curve established with a non-weighted, 4-parameter logistic regression fitting algorithm and the corresponding antibody concentration, corrected for the dilution factor, is expressed in ng/mL.

PCA

The Palivizumab Competitive Assay is based on the competitive binding process between labelled antibody (Palivizumab-biotin) versus non-labelled antibody (Palivizumab-like antibodies in serum) targeting the same epitope on a coated antigen.

First, F protein antigens purified from CHO expression system are coated onto 96-well microplates. Then, after a washing and a blocking step, serial two-fold dilutions of test sera, positive control serum, and Palivizumab antibody reference standard are added in sequence with competitor antibodies (HRP-conjugated Palivizumab) and incubated to allow specific binding of antibodies directed against the F protein antigens. If Palivizumab-like antibodies are present in serum samples, they will compete with the HRP-conjugated Palivizumab antibodies for binding to the F protein coated antigen. After a washing step, the HRP substrate solution (TMB/H₂O₂) is added and a coloured product develops in a manner that is inversely proportional to the amount of Palivizumab-like antibodies contained in the test serum. The colour is quantified by reading the optical densities at 450-620 nm using a spectrophotometer. Antibody concentrations of individual serum and control samples are determined after interpolation from the ELISA standard curve using a four-parameter equation and are expressed as Palivizumab-equivalent antibodies in microgram per millilitre ($\mu\text{g/mL}$).

PCR (Amended 31 July 2017)***Quantitative PCR able to discriminate RSV-A and RSV-B subtypes***

Briefly, RSV A and RSV B RNA extraction from the nasal/throat swabs are detected in a duplex PCR format using specific amplification primers and fluorescent probes designed in the RSV N gene, encoding the RSV nucleocapsid protein. The process involves nucleic acids extractions, conversion of RNA to complementary deoxyribonucleic acid by reverse transcription and detection by real-time PCR reaction using a calibration curve (absolute quantiation). The RSV viral load is reported as copies of RSV RNA per mL of sample.

Qualitative multiplex PCR for detection of a panel of viruses:

A qualitative PCR multiplex assay is used for the detection and identification of multiple respiratory virus nucleic acid in nasal/throat swab from subjects with an assessment visit for MA-RTI. The following virus types and subtypes can be indentified in the assay

- **Influenza A virus (Flu A)**
- **Influenza B virus (Flu B)**
- **Human respiratory syncytial virus A (RSV A)**
- **Human respiratory syncytial virus B (RSV B)**
- **Human Influenza A virus subtype H1 (Flu-A-H1)**
- **Human Influenza A virus subtype H3 (Flu-A-H3)**

- **Human Influenza A virus subtype H1pdm09 (Flu A-H1pdm09)**
- **Human adenovirus (AdV)**
- **Human metapneumovirus (MPV)**
- **Human enterovirus (HEV)**
- **Human parainfluenza virus 1 (PIV1)**
- **Human parainfluenza virus 2 (PIV2)**
- **Human parainfluenza virus 3 (PIV3)**
- **Human parainfluenza virus 4 (PIV4)**
- **Human bocavirus 1/2/3/4 (HBoV)**
- **Human rhinovirus A/B/C (HRV)**
- **Human coronavirus 229E (229E)**
- **Human coronavirus NL63 (NL63)**
- **Human coronavirus OC43 (OC43)**

Following total nucleic acids extraction, viruses are detected by multiplex real-time RT-PCR assays targeting the above mentioned viruses. A comparative analysis of the fluorescence intensities of each target is performed to detect the viruses present in the sample.

This guidance provides you, sponsors, monitors, and investigators of vaccine trials, with recommendations on assessing the severity of clinical and laboratory abnormalities in healthy adult and adolescent volunteers enrolled in clinical trials. The grading system described in the table can also be useful in defining a particular study's stopping rules (e.g., a certain number of AEs, as defined in the table, may call for stopping the study). Less extreme observations (e.g., mild) may not require discontinuing the study vaccine but can still contribute to evaluating safety by identifying parameters to focus upon in subsequent product development. Uniform criteria for categorizing toxicities in healthy volunteers can improve comparisons of safety data among groups within the same study and also between different studies. We, FDA, recommend using toxicity grading scale tables, provided below, as a guideline for selecting the assessment criteria to be used in a clinical trial of a preventive vaccine. We recommend incorporation of such appropriate, uniform, criteria into the investigational plan, case report forms, and study reports and correspondence with FDA, sponsors, monitors, investigators, and IRBs.

This guidance finalizes the draft guidance of the same title dated April 2005 (70 FR 22664, May 2, 2005).

FDA's guidance documents, including this guidance, do not establish legally enforceable responsibilities. Instead, guidances describe FDA's current thinking on a topic and should be viewed only as recommendations, unless specific regulatory or statutory requirements are cited. The use of the word should in FDA's guidances means that something is suggested or recommended, but not required.

- **BACKGROUND**

Standardized toxicity assessment scales have been widely used to evaluate products treating specific diseases. For example, the National Cancer Institute's Common Toxicity Criteria Scale and the Division of AIDS' Toxicity Grading Scale standardize the evaluation of adverse events among patients with cancer and HIV/AIDS, respectively (Refs. 1, 2). The defined toxicity parameters in those scales are designed for patients who may already experience mild, moderate, or severe adverse clinical or laboratory events due to the disease process, and may not be appropriate for healthy volunteers.

In the development of the toxicity grading scales for healthy volunteers, we chose parameter limit values based on published information, when such values were available (Refs. 1-6). For example, the Brighton Collaboration has developed case definitions and guidelines to evaluate some adverse events associated with administering vaccines (Ref. 3). In some cases, parameter limit values were based on clinical experience and experience reviewing vaccine clinical trials that enroll normal healthy subjects.

Toxicity grading scales for laboratory abnormalities should consider the local laboratory reference values when the parameter limit values are defined. The characterization of laboratory parameters among some populations of healthy adults and adolescents may require the exercise of clinical judgment, for example, consideration of the potential for ethnic differences in white blood cell (WBC) counts or gender differences in creatine phosphokinase (CPK) values.

- **TOXICITY GRADING SCALE TABLES**

Adverse events in a clinical trial of an investigational vaccine must be recorded and monitored and, when appropriate, reported to FDA and others involved in an investigation (sponsors, IRBs, and investigators). (See, for example, 21 CFR 312.32, 312.33, 312.50, 312.55, 312.56, 312.60, 312.62, 312.64, and 312.66). Although the use of a toxicity grading scale for adverse events would not replace these regulatory requirements, using a scale to categories adverse events observed during a clinical trial may assist you in monitoring safety and making required reports. Nonetheless, we believe that categorization or grading of data as outlined in this document is supplementary to and should not replace full and complete data analysis.

These guidelines for toxicity grading scales are primarily intended for healthy adult and adolescent volunteers. The parameters in the tables below are not necessarily applicable to every clinical trial of healthy volunteers. The parameters monitored should be appropriate for the specific study vaccine. For some preventive vaccines under development, it may be appropriate to include additional parameters to be monitored during a clinical trial or to alter the choice of values in the toxicity table. For example, additional parameters might be added based on one or more of the following: safety signals observed in pre-clinical toxicology studies, the biological plausibility of the occurrence of certain adverse events, or previous experience with a similar licensed product.

As discussed above, the tables do not represent a recommendation to monitor all the listed parameters in all clinical trials of healthy volunteers, nor do the tables represent all possible parameters to be monitored. In addition, these tables do not represent study inclusion or exclusion criteria. We recommend that the parameters monitored be appropriate for the study vaccine administered to healthy volunteers participating in the clinical trial.

- **Tables for Clinical Abnormalities**

Note from the sponsor: The tables in this section of the guidance will not be used in this particular study. Instead, the parameters as provided in the study protocol are to be used.

- **Tables for Laboratory Abnormalities**

The laboratory values provided in the tables below serve as guidelines and are dependent upon institutional normal parameters. Institutional normal reference ranges should be provided to demonstrate that they are appropriate.

Only those parameters that will be assessed as part of the study have been maintained in the tables below.

Table 23 FDA toxicity grading scales for hematology/biochemistry parameters

Serum*	Mild (Grade 1)	Moderate (Grade 2)	Severe (Grade 3)	Potentially Life Threatening (Grade 4)**
Creatinine – mg/dL	1.5 – 1.7	1.8 – 2.0	2.1 – 2.5	> 2.5 or requires dialysis
Liver Function Tests -ALT, AST increase by factor	1.1 – 2.5 x ULN	2.6 – 5.0 x ULN	5.1 – 10 x ULN	> 10 x ULN
Hematology***				
Hemoglobin (Female) - gm/dL	11.0 – 12.0	9.5 – 10.9	8.0 – 9.4	< 8.0
Hemoglobin (Female) change from baseline value - gm/dL	Any decrease - 1.5	1.6 – 2.0	2.1 – 5.0	> 5.0
WBC Increase - cell/mm ³	10 800 – 15 000	15 001 – 20 000	20 001 – 25 000	> 25 000
WBC Decrease - cell/mm ³	2 500 – 3 500	1 500 – 2 499	1 000 – 1 499	< 1 000
Lymphocytes Decrease - cell/mm ³	750 – 1 000	500 – 749	250 – 499	< 250
Neutrophils Decrease - cell/mm ³	1 500 – 2 000	1 000 – 1 499	500 – 999	< 500
Eosinophils - cell/mm ³	650 – 1 500	1 501 - 5 000	> 5 000	Hypereosinophilic
Platelets Decreased - cell/mm ³	125 000 – 140 000	100 000 – 124 000	25 000 – 99 000	< 25 000

ULN = upper limit of the normal range.

* The laboratory values provided in the tables serve as guidelines and are dependent upon institutional normal parameters. Institutional normal reference ranges should be provided to demonstrate that they are appropriate.

** The clinical signs or symptoms associated with laboratory abnormalities might result in characterization of the laboratory abnormalities as Potentially Life Threatening (Grade 4). For example, a low sodium value that falls within a Grade 3 parameter (125-129 mEq/L) should be recorded as a Grade 4 hyponatremia event if the subject had a new seizure associated with the low sodium value.

*** The laboratory values provided in the tables serve as guidelines and are dependent upon institutional normal parameters. Institutional normal reference ranges should be provided to demonstrate that they are appropriate.

• **REFERENCES for the Appendix D**

1. National Cancer Institute Common Toxicity Criteria, April 30, 1999.
(<http://ctep.cancer.gov/reporting/CTC-3.html>)
2. Division of AIDS Table for Grading Severity of Adult Adverse Experiences; August 1992. (http://rcc.tech-res-intl.com/tox_tables.htm)
3. The Brighton Collaboration. Finalized Case Definitions and Guidelines.
(http://brightoncollaboration.org/internet/en/index/definition___guidelines.html)
4. HIV Vaccine Trials Network Table for Grading Severity of Adverse Experiences; September 18, 2002. (http://rcc.tech-res-intl.com/tox_tables.htm)
5. Division of AIDS Table for Grading the Severity of Adult and Pediatric Adverse Events, December 2004.
(<http://www3.niaid.nih.gov/research/resources/DAIDSClinRsrch/PDF/Safety/DAIDSAEGradingTable.pdf>)

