10.2. Secondary endpoints

- Occurrence of AEs from vaccination up to study conclusion:
 - Occurrence of each solicited local and general AE, during a 7-day follow-up period after vaccination (i.e. the day of vaccination and 6 subsequent days), for all subjects in all groups;
 - Occurrence of any unsolicited AE, during a 30-day follow-up period after vaccination (i.e. the day of vaccination and 29 subsequent days), for all subjects in all groups;
 - Occurrence of any haematological (haemoglobin level, White Blood Cells [WBC], lymphocyte, neutrophil, eosinophil and platelet count) and biochemical

(alanine amino-transferase [ALT], aspartate amino-transferase [AST] and creatinine) laboratory abnormality at Day 0, Day 7, Day 30, Day 60 and Day 90 for all subjects in all groups;

- Occurrence of any SAE, for all subjects in all groups.
- Functional antibody titres against RSV for all subjects in all groups:
 - Neutralising antibody titres against RSV-A at Day 0, Day 30, Day 60 and Day 90;
 - Neutralising antibody titres against RSV-B at Day 0, Day 30, Day 60 and Day 90.
- PCA concentration at Day 0, Day 30, Day 60 and Day 90 for all subjects in all groups.
- Humoral immune response to the residual host cell protein NEO in the investigational RSV vaccine at pre-vaccination (Day 0), and 1 month post-vaccination (Day 30) for all subjects in all groups.
 - Neutralising antibody titres against NEO
- Occurrence of medically attended RSV-associated RTIs up to study conclusion.

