Pregnancy exposures throughout the study and pregnancy outcomes will be described in detail (if applicable).

The percentage of subjects using **concomitant medication** (any medication, any antipyretic and any antipyretic taken prophylactically) during the 7-day (Day 0 to Day 6) or 30-day (Day 0 to Day 29) follow-up period after vaccination will be summarised by group.

For all subjects in each group and each **haematology and biochemistry** parameter:

- The percentage of subjects having haematology and biochemistry results below or above the local laboratory normal ranges will be tabulated for each timepoint.
- The maximum grading post-vaccination (from Day 7 to Day 90) versus baseline (Day 0) and the percentage of subjects with laboratory parameters above or equal to Grade 1, Grade 2, Grade 3 and Grade 4 will be tabulated (Grades will be based on the FDA Guidance for Industry “Toxicity Grading Scale for Healthy Adult and Adolescent Volunteers Enrolled in Preventive Vaccine Clinical Trials”, see [APPENDIX D](#). Those laboratory parameters not included on FDA Toxicity Grading Scale will not be graded).

Assessment of anti-NEO immune response at Day 30 post-vaccination for each group:

- GMCs pre-and post-vaccination will be tabulated with 95% CI and represented graphically.
- Individual post-vaccination *versus* pre-vaccination results will be plotted using scatter plots. Results of the control group will be used as a reference.
- Geometric mean of ratios of antibody concentrations at Day 30 over pre-vaccination will be tabulated with 95% CI.
- Distribution of the antibody concentrations pre-and post-vaccination and of fold increase after vaccination will be tabulated.

Between group evaluation

Exploratory comparisons between each investigational RSV vaccine group and (minus) the control group (*placebo*), and between the RSV vaccine groups (PreF-120 *minus* PreF 30, PreF-120 *minus* PreF-60, PreF-60 *minus* PreF 30) will be done in terms of the

percentage of subjects reporting any \geq Grade 2, Grade 3 AE (solicited and unsolicited), and/or any fever $> 38.5^{\circ}\text{C}$, and/or any vaccine-related SAE during the 7-day follow-up period after vaccination.

The standardised asymptotic 95% CI for the difference between the investigational RSV vaccine groups as well as between the investigational RSV groups and (minus) the control group will be computed.

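### Section 10.9 plans only categorical tabulations of the laboratory data, so a moderate group-wide shift at Day 7 could be missed; summaries of measured values and an exploratory difference from placebo would be a cheap addition

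*Protocol*

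**What the plan says.** The laboratory endpoint in Section 10.2 is binary and per visit: "Occurrence of any haematological (haemoglobin level, White Blood Cells [WBC], lymphocyte, neutrophil, eosinophil and platelet count) and biochemical" (ALT, AST, creatinine) "laboratory abnormality at Day 0, Day 7, Day 30, Day 60 and Day 90 for all subjects in all groups".

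Section 10.9, within-group evaluation, introduces the laboratory analysis with "For all subjects in each group and each" parameter, so placebo is included, and lists two items:

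- An out-of-range table, visit by visit: "The percentage of subjects having haematology and biochemistry results below or above the local laboratory normal ranges will be tabulated for each timepoint".
- A grade table that takes each woman's worst value over the later visits: "The maximum grading post-vaccination (from Day 7 to Day 90) versus baseline (Day 0"), together with the percentage of women at or above each FDA grade.

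The between-group part of Section 10.9 announces "Exploratory comparisons between each investigational RSV vaccine group and (minus) the control group" and between the vaccine groups, with "The standardised asymptotic 95% CI for the difference between the investigational RSV vaccine groups" and for vaccine minus control. The outcomes listed there are Grade 2/3 AEs, fever above 38.5°C and vaccine-related SAEs in the 7-day period. No laboratory parameter is among them.

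Appendix D reprints the FDA guidance used for grading, including the remark that "categorization or grading of data as outlined in this document is supplementary to and should not replace full and complete data analysis".

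**The concern.** All the laboratory information passes through cut-offs. The subjects are healthy women, most of whom should lie well inside the limits, so a shift of the whole group moves few of them across a limit. Grades lose more, because they are reported only as the worst of four visits: an effect confined to Day 7 is mixed with the background of Days 30, 60 and 90.

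This is a stated method and not merely detail left unwritten. The same Section 10.9 sets out measured-value summaries for the other blood-based safety assessment, anti-NEO: geometric means before and after vaccination, and ratios to pre-vaccination, each with a 95% CI. Section 10.7 does likewise for continuous demographics.

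At stake is the sensitivity of a secondary safety endpoint. The 120 µg formulation is given to humans for the first time here, and an acceptable safety profile is a condition for further evaluation, including in pregnant women (Section 1.2.1). A Day 0 value, four later values per woman and a placebo group of about 100 are already collected.

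**Working it through.** **Inputs from the protocol.** About 100 women per group, 1:1:1:1 (Section 5.2.2.2.1). Laboratory samples at Days 0, 7, 30, 60 and 90. Grade 1 ALT starts at 1.1 x ULN (Table 23). Intervals at 95%, which corresponds to two-sided 5%. The protocol gives no laboratory SDs or abnormality rates and plans no test on laboratory data, so the distributions below are assumptions and power serves only as a common yardstick.

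**The plan's own detection figure.** The only one for the step that reviews Day 7 laboratory data is Table 20 (25 per group, at least one event). At 10% incidence, 1 - 0.90^25 = 0.928, as stated; the other six entries also reproduce. It concerns seeing at least one event, not detecting a shift.

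**Check 1: shift of 0.5 SD at Day 7 only, 100 per group.** Assume a normal variable with 2.5% of placebo women beyond the relevant limit.

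- *Day 7 out-of-range percentage.* Vaccine rate = 1 - Φ(1.96 - 0.5) = 7.2%, a difference of 0.047. The standard error is 0.0304 under no difference and 0.0302 under the alternative. Power = Φ((0.047 - 1.96 x 0.0304)/0.0302) = Φ(-0.41) = 34%. With 5% of placebo women out of range (12.6% in the vaccine group) it is 48%. By Fisher's exact test, at the 2.5% placebo rate, it is 22%.
- *Worst of four visits, same cut-off.* With within-woman correlation 0.6, simulated rates are 7.2% and 10.7%. Power = Φ((0.035 - 1.96 x 0.0404)/0.0403) = Φ(-1.09) = 14%. Correlations of 0.4 and 0.8 give the same rounded figure.
- *Day 7 means.* Power = Φ(0.5/√(2/100) - 1.96) = Φ(1.58) = 94%.

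**Other shifts, 100 per group:**

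| Shift | Day 7 out-of-range % (placebo rate 2.5% to 5%) | Day 7 means |
|---|---|---|
| 0.3 SD | 14-19% | 56% |
| 0.5 SD | 34-48% | 94% |
| 0.75 SD | 69-85% | >99% |
| 1.0 SD | 94-99% | >99% |

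**Check 2: ALT +25% at Day 7 only, simulated.** Assumed: log-normal values, median 17-20 U/L, between-woman SD 0.42 and within-woman SD 0.20-0.30 on the log scale, ULN 40 U/L, 100 per group. Detection rates:

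- Grade 1 or worse as maximum over Day 7-90: 11-17%.
- Percentage above ULN at Day 7: 35-54%.
- ANCOVA of log Day 7 value on log Day 0 value and group: 98-100%.

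On these assumptions a 25% rise is ln(1.25) = 0.223 on the log scale, or 0.223/√(0.42² + 0.20²) = 0.48 down to 0.223/√(0.42² + 0.30²) = 0.43 SD, so the two checks describe a similar effect size.

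**The first safety review.** With 25 per group and a 0.5 SD shift, power is 12% on the out-of-range percentage (placebo rate 2.5%) and Φ(0.5/√(2/25) - 1.96) = 42% on means.

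**The case against.** Much can be said for the plan.

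- *The statistical analysis plan may hold these tables.* By-visit descriptive statistics are commonly specified there, and Section 10.9 does not say that its list is exhaustive. This stands as a limit: the protocol does not show that such summaries are unplanned. The point therefore concerns the method that Section 10.9 does set out.
- *Only the grade table is pooled.* Out-of-range percentages are given per visit, which delivers the endpoint as Section 10.2 defines it. This stands.
- *Placebo is tabulated.* A side-by-side comparison exists, and the group comparisons in Section 10.9 are exploratory anyway. This stands; what is not named is an estimated difference with its interval.
- *There are other safeguards.* An unblinded internal committee reviews Day 7 laboratory data at about 25 per group before enrolment resumes (Section 8.10.2), and Grade 3 or higher findings are reported as AEs (Section 8.1.4). Both are real protection against large or severe effects, but less so against a moderate shift. Moreover, Visit 2 falls on Days 7 to 9 (Table 5), after the Day 0-6 window, so a finding first seen there would not normally enter the 7-day AE contrast.
- *Haemoglobin is also graded on change.* True, but any decrease up to 1.5 g/dL is Grade 1. With five exchangeable values and no ties, the chance that at least one of four later values lies below Day 0 is 1 - 1/5 = 80% with no effect at all, so Grade 1 or worse discriminates little.
- *The endpoint concerns abnormalities, and a moderate shift within the normal range may not matter clinically.* Fair. It is a reason to present the values descriptively, not to leave them out.

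**Conclusion.** The point holds as a worthwhile improvement, not as an error that invalidates the laboratory analysis. As written, Section 10.9 is categorical only, pools the grades over four visits, and names no laboratory difference from placebo with an interval. For a moderate Day 7 shift with 100 per group, detection is about 34-54% on the Day 7 out-of-range percentage and 11-17% on the pooled maximum grade, against 94-100% on the values. These figures rest on assumed distributions and would change with the real SDs and abnormality rates; the ordering is the same in both checks.

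Two stronger readings are not supported. A reader might infer that any clear Day 7 effect of the new dose would go unseen. But Day 7 percentages stand alone beside placebo, and shifts of 0.75 to 1.0 SD would be picked up in 69-99% of trials on that table. A reader might also infer that the plan contradicts Appendix D. The remark there is reprinted FDA guidance, which the appendix itself says is to be read as recommendation, and the out-of-range table is in any case an analysis separate from the FDA grades.

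**What to change.** Keep both existing tables and add to the laboratory paragraph of Section 10.9, for each of the nine parameters:

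1. By group and visit, the mean (or geometric mean, for skewed parameters such as ALT, AST and cell counts) and the change (or ratio) from Day 0, with 95% CI.
2. The FDA grade at each visit, next to the maximum-grade table, for parameters that are graded.
3. An exploratory difference or ratio of each RSV group versus control with 95% CI, adjusted for the Day 0 value, at least at Day 7.

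If the statistical analysis plan already contains these, a cross-reference in Section 10.9 is enough.

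The cost is wording and extra tables; no new samples or subjects are needed. The drawback is a set of unadjusted intervals. At Day 7 alone there are 9 x 3 = 27, of which 27 x 0.05 = about 1.4 would exclude no effect by chance. At all four post-vaccination visits there are 9 x 4 x 3 = 108, of which about 5 would. The text should say that they are read descriptively.
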